2.10 IMPLANT RETRIEVAL AND ANALYSIS OF REMOVED IMPLANTS

All available retrieved study implants will be handled and analyzed according to the ASTM Standard F-561-97 (current version) and according to the Exponent, Inc. "Oxford Explant Retrieval Protocol" regarding the handling and analyzing of returned explants. Please refer to **Appendix A** for the *Oxford Explant Retrieval Protocol* and information on how and where to return explanted devices.

2.11 PRIMARY AND SECONDARY STUDY ENDPOINTS

The study's primary safety and efficacy endpoints for the Oxford® Cementless Partial Knee System will include:

• Radiographic Success at 22+ months Study ID: ORTHO.CR.US30

- Absence of Revision/Removal/UADE at any time point
- The Knee Society Assessment Score at 22+ months
- The Knee Society Function Score at 22+ months

The study's secondary endpoints include:

- The Knee Society Assessment Score at all time points other than 22+ months
- The Knee Society Assessment Score for bilateral subjects at all time points
- The Knee Society Function Score at all time points other than 22+ months
- The Knee Society Function Score for bilateral subjects at all time points
- The Oxford Knee Score at all time points
- Radiographic Success at all other time points
- Single question assessment of patient satisfaction at all time points^a

The safety of the system will further be monitored by recording and reporting adverse events [including serious adverse events not considered UADEs throughout the follow-up period].

Safety data will be summarized as follows:

- Device removals or revisions
- Unanticipated adverse device events
- Systemic adverse events
- Local adverse events
- Reoperations and Other Interventions

Any patient who fails to return for multiple, consecutive, scheduled follow-up visits for any reason other than the criteria listed above will be identified as Missing Data.

2.12 END OF ROUTINE STUDY ASSESSMENT

Discontinuation/Withdrawal and Post-Routine Exploratory Patients will be recorded on a Study Completion eCRF (SC100). This case report form is completed when the patient completes the study according to the protocol or if there is a change to the active participation of a patient in the study. Examples include lost-to-follow-up, death, or subject removal of informed consent.

Patients who have had an UADE or a Revision and/or Removal of any Device Component should be followed for safety and patient outcomes according to the visits indicated in this protocol (if possible), for the duration of the study. These patients are considered Post-Routine Exploratory Patients.

_

^a Robertsson, Otta, et al. *Patient Satisfaction Compared With General Health and Disease-Specific Questionnaires in Knee Arthroplasty Patients*. Journal of Arthroplasty, 2001, pp 476-482.

2.13 ANTICIPATED CHANGES

It is anticipated that during the course of the study, certain changes may become desirable. These changes may include additional sizes of components or changes in instrumentation. All changes to the investigation require prior approval from investigator's Institutional Review Board (IRB) or Ethics Committee (EC) and if necessary, the FDA. Any other deviation from the stated protocol will be considered a deviation to the protocol and will be reported accordingly. Changes made to the protocol that are made to protect the life or physical well-being of a patient are considered Emergency Changes and must be reported to the sponsor within 24 hours and to the FDA within 5 days of the sponsor's knowledge of the event. Emergency changes to the protocol are not expected to occur for this device type.

2.14 RADIOGRAPHIC PROTOCOL

A detailed radiographic protocol is contained in Appendix D.

3.0 STATISTICAL ANALYSIS PLAN

This is a two-group, multi-center, randomized clinical trial to compare Biomet's cemented Oxford® Partial Knee System to another active intervention, the Oxford® Cementless Partial Knee System (abbreviations: Control vs. Cementless). Imbalanced, blocked randomization (2:1, Cementless vs. Control) will be implemented.

Randomization will be per patient. In the event that an intraoperative screen failure occurs post-randomization, randomization will not be reassigned and this patient will not count toward the overall sample size. Randomization will continue with the next subject enrolled as previously described. The randomization plan will be produced using SAS v 9.2 for Windows. Randomization will be by center, and each site will receive separate randomization plans using a predetermined block size that will remain undisclosed to the sites. The randomization assignments will be in the form of envelopes to be opened intra-operatively after the first tibial cut and bone quality is assessed against the eligibility criteria.

The primary study endpoint will consist of four (4) individual co-primary endpoints, including both safety and efficacy measures. The following endpoints are included as individual parts of the primary endpoint:

- 1. Knee Society Assessment Score number of points received for the Knee Society Assessment Score at the 22+ month assessment
- 2. Knee Society Function Score number of points received for the Function Score at the 22+ month assessment.
- 3. Revisions or removals of any component of the device or an unanticipated, device-related adverse event (UADE) at any time point. This is a binary endpoint in which a knee is either a "success" or "failure". To obtain a successful result, a knee must reach the 22 + month upper window limit with the device intact and without a component revision/removal or a UADE.
- 4. Radiographic Assessments at the 22+ month assessment

This is a binary endpoint in which a knee is either a "success" or "failure". To obtain a successful radiographic endpoint, a knee must meet the following criteria at the 22+ month

- a. Absence of osteolysis
- b. No migration/subsidence of any femoral or tibial component
- c. Absence of fractured component

Conversely, a radiographic failure is defined as follows:

- a. Presence of osteolysis defined as a radiolucency that is both progressive and is greater than 3 mm at its maximum interface in *two or more* contiguous zones OR a bony destructive lesion that is progressive in nature.
- b. Migration/subsidence of any femoral or tibial component defined as a component migration/subsidence of > 3 mm as compared to 6 week radiographs.
- c. A component fracture

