- 24. Patients who have received systemic steroids within the past 6 months or steroid injection into the affected knee within the previous 6 weeks prior to enrollment
- 25. Patients who are pregnant
- 26. Patients with severe valgus or varus knees (valgus or varus angulation of more than 20°) where collateral ligament, iliotibial band, or popliteal release is required
- 27. Patients who refuse to sign the IRB approved Informed Consent Form
- 28. Participation in an interventional clinical research study procedure, *other than a bilateral knee arthroplasty in this study*, within the past 12 months
- 29. Patients with a history of osteomyelitis or sepsis of the index knee
- 30. Patients who require patellar resurfacing
- 31. Patients who are not skeletally mature
- 32. Patients who have had a total hip replacement procedure <18 months prior to entering the study
- 33. Patients who have had a contralateral non-study knee replacement procedure <18 months prior to entering the study
- 34. Patients who are found intraoperatively to have inadequate bone stock or other conditions that contraindicate a partial knee replacement

NOTE: Patients implanted on the contralateral knee with the investigational or control device as part of their participation in the study are permitted to be enrolled in the study, but will receive a matching device to the original study knee and will not be randomized.

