2.6 RANDOMIZATION

Randomization will not occur until the surgical procedure has commenced. Subjects who have met all eligibility criteria, including the presence of adequate bone stock (see Exclusion #34) following an intraoperative assessment, and have signed the IRB-approved informed consent will be randomly assigned to one of two treatment groups. Patients will be randomized using a 2:1 randomization scheme for investigational:control devices. The randomization plan will be produced using SAS v 9.2 for Windows. Sequentially numbered envelopes will be provided to

each study site to implement randomization. See the Statistical Analysis Plan section for a specific description of the randomization scheme.

The sponsor will review the following preoperative eligibility paperwork: Informed Consent, Historical Record and pre-operative Knee Society Assessment score prior to enrollment in the study and approve randomization for a subject. Control and accountability of the investigational device will be managed in accordance with the sponsor's most current procedure for device accountability.

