3.4.2. INTENT TO TREAT (ITT) POPULATION

Patients who have met the Inclusion/Exclusion criteria, signed the Informed Consent, and been randomized comprise the ITT population and will be tracked. Those patients that have "fallen out" of the study and did not receive either the investigational or the control device will be summarized by specific reason for not receiving the study device. The primary endpoint will be analyzed for the ITT Population as a sensitivity analysis, with the purpose of evaluating the impact of protocol deviations and missing data on the primary endpoints.

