3.5.2. ANALYSES OF STUDY POPULATION

Analysis for primary and secondary endpoints will use the Per Protocol population, which consists of those cases with complete data for one or more of the primary endpoints collected per the protocol at the 22+ month follow-up visit (or, as described below in the section on Missing Data, at the last or next available visit if the primary endpoint in question is missing at the 24- month visit). The exception to this is the primary endpoint of Absence of Revision/Removal/UADE, which is cumulative; therefore all cases that have failed at or prior to 24 months due to a revision or UADE will be included in the analysis of that primary endpoint. For each primary endpoint, all available data will be used, even if the subject has missing data for one or more of the other endpoints. Since indications and inclusion/exclusion criteria are exactly the same for both device groups, and because randomization is received at the time of surgery, it is expected that few patients will fail to receive the assigned treatment. However, in the event that they do not, the primary analysis will use the device that was actually implanted if it was a study device; if a study device is not received, the patient will not be included in the primary analysis.

Bilateral patients will be used in the primary analysis for the of Radiographic Success and Absence of Revision/Removal/UADE endpoints, but will be analyzed separately for the Knee Society Function and Assessment endpoints. The bilateral patients will not be included in the primary analysis for the Knee Score endpoints, as there is no way to ensure that the knee scores for one knee will not be affected by the other. The sample size has been increased by 10% to allow for this, a percentage based on the bilateral enrollment in the post-approval study for the OxfordTM Menisal Unicompartmental Knee System.

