4.2. GENERAL RISKS ASSOCIATED PARTIAL KNEE REPLACEMENT

- 1. Early or late infection perhaps necessitating device removal
- 2. Component dislocation
- 3. Fracture or perforation of the bone or device (intraoperative or post-operative)
- 4. Device loosening or migration
- 5. Valgus/Varus deformity
- 6. Inadequate lubrication
- 7. Patellar tendon rupture and ligamentous laxity
- 8. Fretting or corrosion of implant interfaces
- 9. Wear and/or deformation of articulating surfaces
- 10. Particulate wear debris may initiate a cellular response leading to osteolysis
- 11. Damage to surrounding tissues, cartilage, or tendons
- 12. Inadequate range of motion
- 13. Persistent pain

- 14. Progression of the disease in the lateral compartment necessitating revision
- 15. Transient peroneal palsy secondary to surgical manipulation and increased joint movement
- 16. Implantation of the device may require greater surgical exposure and prolonged surgical time
- 17. Instability
- 18. Peripheral neuropathies, heterotopic bone formation and/or histological reactions which may occur with or without clinical significance
- 19. Failure of cement fixation resulting in loosening of the implant

Rarely some adverse events may be fatal. These possible adverse events are not unique to the Oxford® Cementless Knee System and, as stated above, may occur with any partial joint replacement surgery.

Limitations may be imposed depending upon the patient's age, general health, baseline (preoperative) activity level and baseline (preoperative) condition of the knee and other joints.

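### A screen failure declared after the envelope is opened leaves the sample size, the primary analysis if no study device is implanted, and apparently the ITT set

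*Combined protocol and SAP*

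**What the plan says.** **Before opening.** Section 2.6 assigns treatment to "Subjects who have met all eligibility criteria, including the presence of adequate bone stock", as judged during surgery. Section 3.0 agrees: envelopes are "opened intra-operatively after the first tibial cut and bone quality is assessed against the eligibility criteria".

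**After opening.** Section 3.0 still provides for the case in which an "intraoperative screen failure occurs post-randomization, randomization will not be reassigned and this patient will not count toward the overall sample size". Enrolment then continues with the next subject. The documents do not define intraoperative screen failure. The only intraoperative exclusion is number 34 in Section 2.2: "Patients who are found intraoperatively to have inadequate bone stock or other conditions that contraindicate a partial knee replacement". It carries no time limit of its own.

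**Analysis sets.** The primary analysis is per protocol and by the device implanted. Section 3.5.2 adds that "if a study device is not received, the patient will not be included in the primary analysis". Section 3.4.2 defines ITT: "Patients who have met the Inclusion/Exclusion criteria, signed the Informed Consent, and been randomized comprise the ITT population". It promises a summary, by reason, of patients who received neither device, and makes the ITT analysis a sensitivity analysis. Appendix B confirms that analysis by assigned treatment appears only there, and that blinding is single because of the nature of the device.

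**The concern.** If eligibility is settled before the envelope is opened, nobody should become a screen failure afterwards. The plan nevertheless expects that some may. It does not say what qualifies, who decides, or that the decision is made without knowledge of the allocation. In practice the decision presumably falls to the operating surgeon, who has just seen the assignment.

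The primary analysis already follows the implanted device, so ITT is the one planned comparison that respects the randomization. If ITT carries the same eligibility filter, an exclusion made after allocation is absent from both analyses. A knee that was hard to fit with the assigned component could then leave the comparison under the label of ineligibility.

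Two neighbouring cases are loosely specified. An eligible patient whose implant attempt fails remains in ITT, but Section 3.4.2 does not say how a knee with no study device is scored. A Cementless attempt converted to the cemented study device is analysed under Control in the primary analysis, which takes a failed attempt out of the Cementless arm.

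**Working it through.** **1. Where each kind of patient goes.**

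| Case after opening | Sample size | Primary analysis | ITT |
|---|---|---|---|
| Declared screen failure, no study device | Out (3.0, stated) | Out (3.5.2, stated) | Apparently out (inferred from 3.4.2 and exclusion 34) |
| Eligible, attempt fails, no study device | Not addressed | Out (3.5.2, stated) | In; scoring not stated |
| Cementless attempt converted to cemented study device | Not addressed | In, under Control (3.5.2) | In, under Cementless (Appendix B: by assigned treatment) |

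**2. The plan's sample size.** Inputs from Section 3.3: 95% success in both arms, margin 0.08, one-sided α 0.05, power 90%, ratio 2:1.

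- Control: (1.645 + 1.282)² × (0.0475 + 0.0475/2) / 0.08² = 8.564 × 0.07125 / 0.0064 = 95.3, so 96.
- Cementless: twice 95.34 = 190.7, so 191.
- Dividing by 1 − 0.25 gives 96/0.75 = 128 and 191/0.75 = 254.7, so 255; the total is 383.

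The stated figures reproduce, so this point does not rest on a sample-size error. Post-opening screen failures do not count toward N, so they do not reduce the number analysed.

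**3. Sensitivity of the radiographic test.** The bound is that of Section 3.2: (p_C − p_I) + 1.645 × √(SE_C² + SE_I²).

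Assumptions: 255 and 128 less 15% attrition give 216.75 and 108.8, taken as 217 and 109. Observed success is 95% in both arms. The k excluded Cementless knees are added back as failures, so p_I = 0.95 × 217/(217 + k) and n_I = 217 + k. The c excluded Control knees are treated the same way.

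For k = 9, c = 0: p_I = 206.15/226 = 0.9122, SE_C = 0.0209, SE_I = 0.0188, and the bound is 0.0378 + 1.645 × 0.0281 = 0.0841.

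| k Cementless | Share of Cementless | c Control | Upper bound | Within 0.08? |
|---|---|---|---|---|
| 0 | 0% | 0 | 0.0421 | Yes |
| 5 | 2.3% | 0 | 0.0660 | Yes |
| 8 | 3.6% | 0 | 0.0796 | Just |
| 9 | 4.0% | 0 | 0.0841 | No |
| 9 | 4.0% | 1 | 0.0773 | Yes |
| 9 | 4.0% | 2 | 0.0706 | Yes |
| 9 | 4.0% | 4 | 0.0571 | Yes |

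At the plan's unadjusted numbers (91/96 v 181/191 successes), 6 Cementless exclusions give 0.078 and 7 (3.5%) give 0.083.

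**4. Effect on false non-inferiority.** Suppose Control success is 95%, and Cementless success with exclusions counted as failures is 87%, exactly at the margin. If a share f of Cementless allocations is removed and replaced, the analysed rate is 0.87/(1 − f). The table gives the chance of passing the 8% test at 191 v 96, by exact binomial enumeration.

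| f | Analysed rate | Chance of passing |
|---|---|---|
| 0% | 0.870 | 4.4% |
| 1% | 0.879 | 7.7% |
| 2% | 0.888 | 13.0% |
| 3% | 0.897 | 21.0% |
| 5% | 0.916 | 46.6% |

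The documents give no value for f; the 0–5% range is an assumption.

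**The case against.** The strongest reply is that the plan puts the bone-quality check before the envelope is opened, in both Section 2.6 and Section 3.0. The criterion most likely to bear differently on press-fit and cemented fixation is thus applied before allocation. What remains is the second half of exclusion 34, which concerns partial replacement in either arm. Section 3.5.2 also expects few patients to miss their assigned treatment. This stands: it should keep numbers small, and it means the direction of bias is conjecture. It does not remove the gap, because Section 3.0 still provides for the later screen failure without defining, limiting or adjudicating it.

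A reader might infer four stronger things that the documents do not support:

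- *That the plan states these patients leave ITT.* It does not. The reading follows from the eligibility condition in Section 3.4.2; it is a strong inference, but only that.
- *That every failed implant attempt disappears from all co-primary endpoints.* A knee that fractures during implantation, a risk listed in Section 4.2, may belong to an eligible, randomized patient, who stays in ITT. Section 3.0 requires the device to be intact for success on the revision endpoint, so that knee would be a failure or missing. If missing, the worst-case and tipping-point analyses of Section 3.5.5 are available. A conversion to the cemented study device is counted, under Control.
- *That reporting by arm is ruled out.* Section 3.4.2 specifies a summary by reason and is silent on arm.
- *That nine exclusions would overturn the result.* That needs every one to be in Cementless and every one to be a failure. A single Control exclusion reverses it.

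**Conclusion.** The concern holds in limited form. Removal from the sample size is stated, as is removal from the primary analysis when no study device is received. Removal from ITT is the natural reading but is not written. Because the label is undefined and partly discretionary, a surgeon who knows the allocation could exclude a patient, and the ITT sensitivity analysis might not reveal it.

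The size is unknown, since the documents give no exclusion rate. Under the one-sided assumptions above, about 3.5% to 4% of Cementless allocations would be enough to carry the radiographic bound past its margin. Removal of 2% would raise the chance of a false non-inferiority finding on that test from 4.4% to 13.0%. Both figures describe an unfavourable scenario and are not forecasts; exclusions in Control shrink the effect quickly. The point merits a change to the plan because the remedy is cheap and the ITT analysis is the only planned check by assigned arm.

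**What to change.** 1. Define ITT as every patient whose envelope was opened, analysed in the assigned arm.
2. State that eligibility for analysis closes at opening. A patient later found unsuitable may be replaced for accrual but is not removed from ITT. This governs the analysis sets only and does not touch the surgeon's decisions during the operation.
3. Report post-opening exclusions, and non-receipt of the assigned device, by arm and reason.
4. Add an ITT sensitivity analysis of Radiographic Success and Absence of Revision/Removal/UADE. Count knees with no study device as failures in the assigned arm, and Cementless-to-cemented conversions as Cementless failures.
5. Keep this as a sensitivity analysis. Requiring it to meet the margins would add a success criterion and affect power, which is a separate and debatable decision.

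The cost is revised wording in Sections 3.0, 3.4.2 and 3.5.5, one more table and one more analysis. The sample size does not change. The downside for the sponsor is that Cementless success may look slightly less favourable.

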3.1.1. RADIOGRAPHIC SUCCESS

The proportion of radiographically successful knees in the Cementless group is non-inferior to the proportion of radiographically successful knees in the Control group using an 8% margin of non-inferiority. The test is based on the upper bound of a one-sided 95% confidence interval for the difference, Control minus Cementless, of proportions of success at 22+ months. A conclusion of non-inferiority is supported if the upper bound of the confidence interval is 0.08 or less. In addition, a Fisher's Exact p-value will also be computed to test this hypothesis.

In this analysis, each knee will be considered as a separate case, and unilateral and bilateral subjects will be analyzed together, providing the unilateral and bilateral groups are poolable per sensitivity analyses given in Section 3.1.5°.

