3.3 SAMPLE SIZE JUSTIFICATION

In order to calculate the sample size for this study, the sample size needed to obtain 90% power for each primary endpoint was calculated. The endpoint requiring the largest sample size to maintain 90% power was Radiographic Success. Therefore, this is the sample size used in this study to ensure that we have a sufficient number of knees/patients to test each of the four primary endpoints with at least 90% power.

The sample size for the radiographic success primary endpoint was calculated as follows:

Let p_I and p_C denote the true population proportions of a successful outcome in the Cementless and Control groups, respectively.

Under H_0 , p_C is markedly larger than p_I and the Cementless device is inferior. Contrarily, under H_1 , this is not true and the true proportion of success for the Cementless device is, at worst, δ less than for the Control. We have δ = 0.08 (i.e., 8%).

Information about plausible values of the proportions p_I and p_C is available in the SSED for the LPS Flex Mobile Device (PMA #P060037). This document was used to help estimate the percentage of radiographic success for sample size purposes because it used a similar radiographic success/failure endpoint as the one given in this protocol. For purposes of the sample size calculation, we use the radiographic failure rates in Table 5 (page 18-19) of the document. This shows a 1.2% radiographic failure rate for the investigational device and a 2.4% radiographic failure rate for the control. Since we have slightly different radiographic success criteria, and because we want to ensure that we have adequate power for testing this endpoint, we will use 5% as our estimate of radiographic failure, giving a 95% estimate of radiographic success.

Assuming 95% to be the true, equal values of p_1 and p_2 , non-inferiority sample size calculations were implemented in nQuery Advisor 7.0 software using a 2:1 ratio of Cementless to Control subjects. This software uses methodology as described in an article by Farrington and Manning^e.

Definitions:

 p_l : Proportion of successes in the Experimental (Oxford Cementless) treatment group.

 $p_{\mathcal{C}}$: Proportion of success in the Control (Oxford Cemented) treatment group.

For a specified constant, $0 < \delta < 1$, the hypotheses of non-inferiority are:

$$H_0: p_C - p_I > \delta \text{ vs. } H_1: p_C - p_I \leq \delta.$$

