APPENDIX A – OXFORD EXPLANT RETRIEVAL PROTOCOL

APPENDIX B-ANALYSIS OF SCIENTIFIC SOUNDNESS

Trial Objectives	The trial objectives are clear and concise and provide a basis for labeling indications for subsequent PMA submission.
Selection of Variables	 Outcome variables are controlled with carefully defined primary study endpoints. The endpoints are directly observable, objectively determined, and designed to reduce bias and error. Influencing variables are controlled by the use of identical inclusion/exclusion criteria for the control and study populations. An extensive search of available literature and consultation with experts in the field were undertaken to discuss potential influencing variables (age, weight, gender, etc.) and these variables are not anticipated to effect study outcome.
Study Population	Inclusion/exclusion criteria have been developed by clinical experts and designers of the device. They are unambiguous and appropriately assess prognostic factors that may affect outcome variables.
Control Population	Concurrent controls are being used for this study. Control subjects will be assigned an alternative intervention and will remain under the direct care of the clinical study investigator.
Methods of Assigning Interventions	Blocked randomization will be used to assign intervention. A validated electronic system will be used to perform randomization.
Scientific Trial Design	The protocol addresses the treatment of study data that results from major and minor protocol deviations.
Sample Size Justification and Statistical Power	nQuery Advisor v. 7.0 was used to calculate the sample size for this study. Sample size calculation details are specified clearly in the analysis plan, and used 90% power, 5% Type I Error, and an 8% non-inferiority margin.
Blinding	Single blinding is being used in this study to avoid biased outcomes. Double and third party blinding cannot be undertaken due to the nature of the device. Secondary endpoints have been designed to further decrease potential bias.
Study Site and Investigator	Study sites and investigators have been carefully chosen for the study based on sufficient numbers of eligible patients, adequate facilities to support the protocol, prior clinical trial experience, and device specific experience.
Trial Monitoring	Trial monitoring plans are outlined in the protocol and supporting documents.
Baseline Evaluation	Baseline evaluations will be performed prior to subject entry

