	into the trial. Six week follow up radiographs will serve as baseline for radiographic endpoints.
Intervention	Randomization will be performed with the use of a validated electronic system under the control of the Sponsor to ensure strict adherence to the protocol.
Follow Up	Mechanisms are in place to ensure that a high degree of subject compliance is maintained. Exclusion criteria have been designed to increase the likelihood of follow up by limiting disease states and other conditions that may interfere with the proposed follow up time period. The minimum duration of follow-up is two years. This is sufficient to capture anticipated effectiveness and to accurately estimate the rate of known or suspected adverse events. The duration of follow-up is identical for study and control populations.
Collection and Validation of Data	Validated methods for capturing data are currently in place and will be monitored for compliance throughout the trial.
Validation of Assumptions	Assumptions made for statistical methods will be checked before beginning a detailed analysis using these methods. If assumptions are not met, more appropriate tests will be used (e.g. non-parametric methods).
Hypothesis and Statistical Tests	The protocol clearly states the hypotheses to be tested and statistical tests to be used.
Pooling	Pooling is justified based on inclusion/exclusion criteria and adherence to the protocol will be strictly monitored and enforced to further justify pooling of study data.
Intent-to-Treat Analysis	An analysis of patients by the assigned treatment will be conducted in the sensitivity analyses for this study.

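### Site envelopes from lists with a single undisclosed block size, opened just after a discretionary bone-stock judgment, leave room for selection, and Appendix B describes a different allocation mechanism

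*Combined protocol and SAP*

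**What the plan says.** **Lists.** Section 3.0 specifies blocked 2:1 randomization (Cementless to Control) by center: "each site will receive separate randomization plans using a predetermined block size that will remain undisclosed to the sites". The block size is in the singular and its value is not given.

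**Delivery.** Section 2.6: "Sequentially numbered envelopes will be provided to" each study site. Section 3.0 says that the envelopes are "opened intra-operatively after the first tibial cut and bone quality is assessed against the eligibility criteria". The documents do not say who holds the envelopes, whether they are opaque and sealed, or whether the bone-stock decision is written down before opening.

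**The last eligibility decision.** Exclusion 34 (Section 2.2) covers inadequate bone stock, or any other condition found at surgery that rules out a partial knee. Sponsor approval under Section 2.6 rests on the consent form, the history and the preoperative Knee Society Assessment score, all of which precede surgery.

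**After randomization.** Section 3.0 provides that a patient who becomes an intraoperative screen failure once randomized keeps the assignment but does not count toward the sample size. Under Section 3.5.2, a patient who receives no study device is left out of the primary analysis.

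**Blinding.** The trial is single-blind. Appendix B says that double and third-party blinding are not possible with this device.

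**Appendix B (Intervention row).** "Randomization will be performed with the use of a validated electronic system under the control of the Sponsor". The row on assigning interventions also names a validated electronic system.

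**The concern.** There are two separate issues.

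The first is concealment. Site envelopes and a sponsor-controlled electronic system offer different protection. With the system, the sponsor can require that eligibility be entered before the assignment appears. With envelopes, that depends on conduct at the site. The text supports both descriptions and does not choose between them.

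The second is predictability. Within a site, permuted blocks of constant size leave some allocations fixed by those before them. The final eligibility decision is a judgment made moments before opening, by staff who see the devices implanted. Someone who expects a particular device could rule a borderline knee in or out accordingly. A patient excluded in this way is never randomized and appears in no analysis population, including the ITT population of Section 3.4.2. The allowance for screen failures after randomization adds a second route, in which the decision is made with the assignment already seen. In a non-inferiority comparison, selection of this kind can move the difference toward or away from the margin.

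**Working it through.** **The plan's own figures.** The documents give no figure for predictability. The sample size serves here only as a denominator, and it reproduces. The inputs are 95% success in both arms, margin 0.08, one-sided alpha 0.05, power 0.90 and 2:1 allocation (Sections 3.1.1 and 3.3). Control n = (1.645 + 1.282)² × (0.0475 + 0.0475/2) / 0.08² ≈ 95.3, so 96. Cementless n = 2 × 95.3 = 190.7, so 191. Dividing the total of 287 by 0.75 (10% bilateral allowance and 15% attrition) gives 382.7, so 383. None of this is in dispute.

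**Assumptions for predictability.** Block sizes of 3, 6, 9 and 12 are assumed, because the documents give none. The observer is assumed to know the block size and every earlier allocation at the site. That is the worst case.

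**Formula.** Take a block of *a* Cementless and *b* Control. An allocation is certain once only one device remains. The expected number of Cementless left after the last Control is a/(b+1), and of Control left after the last Cementless is b/(a+1). The certain share is therefore [a/(b+1) + b/(a+1)] / (a+b).

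**Block of 3 by hand** (I = Cementless, C = Control). The three orders are CII, ICI and IIC. The certain positions number 2, 1 and 1, so 4 of 9 = 44.4%. To guess best, name the device with more left in the block and score a tie as one half. This gives 2, 2.5 and 2.5 correct, so 7 of 9 = 77.8%.

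| Block | Certain share | Of 383 | Best-guess accuracy | Gain over always guessing Cementless (66.7%) |
|---|---|---|---|---|
| 3 | (2/2 + 1/3)/3 = 44.4% | 170 | 77.8% | 11.1 points |
| 6 | (4/3 + 2/5)/6 = 28.9% | 111 | 74.4% | 7.7 points |
| 9 | (6/4 + 3/7)/9 = 21.4% | 82 | 72.7% | 6.0 points |
| 12 | (8/5 + 4/9)/12 = 17.0% | 65 | 71.7% | 5.0 points |

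Full enumeration of the sequences gives the same certain shares. The counts out of 383 are upper limits, because 383 is a number of knees and a second study knee is matched to the first rather than randomized (note to Section 2.2).

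**Randomly varied sizes.** This was simulated with 32 patients per site (383/12 = 31.9 if all 12 sites in Section 2.4 enroll equally) and 1,500 sites per setting. The observer knows which sizes are in use but not their order.

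| Sizes | Certain share | Best-guess accuracy |
|---|---|---|
| 3 only | 42.7% | 76.9% |
| 6 only | 26.9% | 74.1% |
| 9 only | 18.0% | 71.9% |
| 3 and 6 | 9.7% | 75.0% |
| 6 and 9 | 5.5% | 72.6% |
| 3, 6 and 9 | 3.5% | 73.1% |

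The single-size rows fall a little below the closed form because a site's last block may be incomplete. Varying the size removes most of the certainty but barely changes best-guess accuracy.

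**Order of events.** Sections 2.6 and 3.0 both place the bone-stock check before the envelope. If that order always held, an intraoperative screen failure after randomization should be rare. Section 3.0 nonetheless provides for one, and nothing requires the earlier decision to be on record.

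**The case against.** Blocked, center-stratified envelopes with a block size withheld from sites are a workable design, and withholding the size is a real safeguard. The percentages apply only to a site that has deduced the size and knows every earlier assignment. Even then the gain over always guessing Cementless is 5 to 11 points. This stands, and the figures should be read as ceilings.

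A reader might infer that the surgeons hold the envelopes and know the whole allocation history. The documents say only that envelopes go to sites. They name no custodian and do not say that each site has one surgeon. A surgeon sees the devices that he or she implants, and no more can be assumed. The singular block size is the natural reading, but sizes could still differ between sites.

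A reader might also infer that the Appendix B conflict makes allocations predictable. It does not: an electronic system using the same blocks would be just as predictable from past assignments. The conflict bears on concealment. It may be loose wording for producing the list in SAS on the sponsor's side. However, Appendix B says that randomization is performed by the system, so a clarification is still needed.

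Finally, a reader might infer that the bias favours Cementless. Section 4.3 lists failure of biologic fixation as a risk of the cementless device, and migration is part of the radiographic endpoint, so that direction is plausible. But exclusion 34 concerns partial knees of either kind, and nothing shows how investigators would lean. The baseline comparisons (Section 3.5.1) and regressions (Section 3.5.6) could reveal measured imbalance, but bone quality is not among the variables they list.

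**Conclusion.** The point holds as a minor one. The text leaves the concealment mechanism unsettled, places a discretionary exclusion directly before the assignment, and allows exclusion after it. That creates a risk of selection that could favour either arm. It is not evidence that selection occurred, and the documents do not support saying that many allocations are predictable in practice.

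On size: if a site deduced a constant block size and knew all earlier allocations, at most 17% (block of 12) to 44% (block of 3) would be certain. These figures rest on assumed block sizes and a fully informed observer. If the size stays unknown to the site, fewer are certain. The contradiction with Appendix B and the gap after randomization rest on no such assumption.

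**What to change.** 1. For any remaining enrolment, generate each site's list with randomly varying block sizes. Certain predictions fall to about 4-10%. Best-guess accuracy stays about 73-75%, so this step is only a partial remedy.
2. Require the intraoperative eligibility decision to be recorded before the assignment is released, through the electronic system if it exists. This closes the route by which a seen assignment could influence exclusion, and it leaves a record of exclusions made in theatre. It does not by itself prevent a decision based on an expected assignment, which is why step 1 is also needed.
3. Reconcile Sections 2.6 and 3.0 with Appendix B, and state which mechanism was used. If envelopes, say who holds them and how they are sealed and logged.

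The cost is a short amendment, regenerated lists or envelopes, and slightly looser 2:1 balance within a site. Sample size, endpoints and treatment do not change. The document is version 7.0 of June 2016 and does not say how many patients remain to be randomized. If enrolment is complete, only step 3 applies.
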